4.2.1.2.5 Duration

Duration is derived from the start and end dates of the unsolicited AE:

- Duration = stop date of unsolicited AE - start date of unsolicited AE + 1.

The duration should be considered as missing only if one of or both the start and end dates of the unsolicited AE is missing or partially missing.

Main analysis, sensitivity analysis and complementary analysis will be applied by duration. The duration for sensitivity analysis and complementary analysis is derived by the general method mentioned above. Suppose a participant receiving an authorized/approved COVID-19 vaccine on Day X, the duration for main analysis is derived as follows:

- If an unsolicited AE for the participant with both time of onset and stop date before Day X, then the duration for that AE will be derived same as above.
- If an unsolicited AE for the participant with time of onset before Day X and the corresponding stop date is on or after Day X, then the duration will be derived as Missing.

Duration will be categorized into and displayed as 1-3 days, 4-7 days, 8 days or more, and Missing.

4.2.1.2.6 Medically-Attended Adverse Event

An event will be considered as an MAAE if “Yes” is checked for “Is the event an MAAE?” in the CRF. MAAEs will be analyzed throughout the study using the following periods:

For Supplemental Cohort 1 and Cohort 2 booster arms:

- From D01 to 21 days post dose 1
- During the 6 months follow up period
- During the entire study (ie, all MAAEs occurred during the study)

For Supplemental Cohorts Comparator Group:

- D01 to dose 2 (including the day of dose 2, use 21 days after D01 if dose 2 is not received)
- Within 21 days post dose 2
- From D01 to 21 days post dose 2

- During the 6 months follow up period
- During the entire study (ie, all MAAEs occurred during the study)

Note: MAAE that occurred before vaccination (negative time of onset) will not be included in analysis but will be listed separately.

Main analysis and complementary analysis will be applied for MAAEs.

4.2.1.2.7 Serious Adverse Events

An event will be considered as a serious event if “Yes” is checked for “Serious” in the CRF.

SAEs will be analyzed throughout the study using the following periods:

For Supplemental Cohort 1 and Cohort 2 booster arms:

- From D01 to 21 days post dose 1
- During the 6 months follow up period
- During the entire study (ie, all SAEs occurred during the study)

For Supplemental Cohorts Comparator Group:

- D01 to dose 2 (including the day of dose 2, use 21 days after D01 if dose 2 is not received)
- Within 21 days post dose 2
- From D01 to 21 days post dose 2
- During the 6 months follow up period
- During the entire study (ie, all SAEs occurred during the study)

Note: SAE that occurred before vaccination (negative time of onset) will not be included in analysis but will be listed separately.

Main analysis and complementary analysis will be applied for SAEs.

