4.2.1.2 Unsolicited AEs

Unsolicited AEs include unsolicited non-serious AEs, immediate unsolicited AEs, SAEs, AESIs and MAAEs. Analysis for unsolicited AEs only include those AEs collected within 21 days after each injection. SAEs, AESIs and MAAEs collected out of this range will only be presented in the analysis of SAEs/AESIs and MAAEs.

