4.2.1.2.3 Last Vaccination

The last vaccination before an unsolicited AE is derived from the start date of the unsolicited AE provided in the clinical database and is calculated as follows:

- If an unsolicited AE has a complete start date and different to any of the vaccination dates, the start date is used to determine the last vaccination before the unsolicited AE.
- If the start date is missing or partially missing, or equal to any vaccination date, then the visit number in the “Appeared after Visit” or similar field, is used to determine the last vaccination before the unsolicited AE.

NOTE: This vaccination refers to the last study vaccination and not to a non-study authorized/approved COVID-19 vaccination.

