4.2.1.2.4 Time of Onset

Time of onset is derived from the start date of the unsolicited AE provided in the clinical database and the date of last vaccination as described in [Section 4.2.1.2.3](#):

- Time of onset = start date of the unsolicited AE – date of last vaccination before the unsolicited AE + 1

The time of onset should be considered as missing only if one of or both the dates are missing or partially missing.

The unsolicited AEs will be analyzed “Within 21 days”, which corresponds to AEs with a time of onset between 1 and 22 days or missing.

An AE with missing time of onset will be considered to have occurred just after the vaccination indicated by the visit number in “Appeared after visit” or similar field, so will be included in these tables.

Time of onset will be categorized into and displayed as 1-4 days, 5-8 days, 9-15 days, 16 days or later, and Missing.

Note: To further clarify the analysis:

- Any unsolicited AEs collected throughout the study (SAEs, MAAEs, AESIs) with time of onset > 22 days after each injection will not be presented in tables of unsolicited AEs within 21 days but only in tables of SAEs, MAAEs, AESIs.

- Any unsolicited AEs (planned to report up to 21 days) with time of onset between 1 and 22 days or missing after each injection will be presented in the tables of unsolicited AEs within 21 days.
- Any unsolicited AEs (planned to report up to 21 days) with time of onset > 22 days after the 1st injection will not be presented in any tables but listed separately.
- Any unsolicited AEs with null (0) or negative time of onset will be excluded from the above tables and listed separately.

Main analysis and complementary analysis will be applied by time of onset.

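### In the Comparator Group, the by-dose periods for SAEs, AESIs and MAAEs overlap on the day of dose 2, so a post-injection event that day is also counted in the dose 1 row

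*SAP*

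**What the plan says.** Three subsections of the SAP use identical wording for the Comparator Group: 4.2.1.2.6 (MAAEs), 4.2.1.2.7 (SAEs) and 4.2.1.2.8 (AESIs). The first period is "D01 to dose 2 (including the day of dose 2, use 21 days after D01 if dose 2 is not received"). The second is "Within 21 days post dose 2", and these subsections do not give its start day. A combined period from D01 to 21 days after dose 2, a six-month period and an entire-study period follow.

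The general rules for unsolicited AEs come earlier in section 4.2.1.2, and their scope is explicit: "Unsolicited AEs include unsolicited non-serious AEs, immediate unsolicited AEs, SAEs, AESIs and MAAEs".

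- Section 4.2.1.2.3 covers events that start on an injection day. "If the start date is missing or partially missing, or equal to any vaccination date", the visit number in the 'Appeared after Visit' field "is used to determine the last vaccination before the unsolicited AE".
- Section 4.2.1.2.4 fixes the day count: "Time of onset = start date of the unsolicited AE – date of last vaccination before the unsolicited AE + 1". It then defines the 21-day window, "which corresponds to AEs with a time of onset between 1 and 22 days or missing".

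**The concern.** One part of the SAP splits the injection day by whether the event came before or after the injection. The other places the whole calendar day in the earlier period.

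Take a Comparator participant with an acute allergic AESI one hour after dose 2. By section 4.2.1.2.3 the last vaccination is dose 2, and by section 4.2.1.2.4 the onset day is 1. The unsolicited AE tables therefore show the event under dose 2. The AESI table, programmed by date from the wording of 4.2.1.2.8, shows it in the period meant to describe dose 1.

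The injection day is when an acute reaction to the vaccine is most plausible, so the ambiguity falls on the day that matters most for attribution by dose. Section 3.3 also commits the safety analysis set to analysis after each dose. Two programmers could produce different by-dose tables from this text, and one of those tables would disagree with the unsolicited AE output.

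**Working it through.** **Inputs, all from the SAP**
- Dose 2 is planned at D22 (section 1, text after Table 1.3).
- Onset day = start date − date of last vaccination + 1; the 21-day window is onset days 1 to 22 (section 4.2.1.2.4).
- Comparator safety data are required up to D43 for the interim analyses (section 3.5).
- Planned Comparator size is 515 (Table 1.2).

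**Reproducing the plan's own figure.** With dose 2 on D22, onset day 1 is D22 and onset day 22 is D22 + 21 = D43. This matches the D43 in section 3.5, so the day-1 convention fits the rest of the SAP.

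**Comparing the periods**

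| Period | Days | Length |
|---|---|---|
| First (D01 to dose 2, that day included) | D01-D22 | 22 |
| Second (21 days post dose 2, window of 4.2.1.2.4) | D22-D43 | 22 |
| Combined | D01-D43 | 43 |

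22 + 22 = 44, and 44 − 43 = 1. The overlap is one day, D22. A post-injection event on D22 falls in both dose periods.

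**Alternative start day.** If the second period began the day after dose 2, it would be D23-D43 (21 days), and 22 + 21 = 43 with no overlap. Every D22 event would then sit only in the first period, including those after the injection. That conflicts with sections 4.2.1.2.3 and 4.2.1.2.4.

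**After the correction.** On whole days, D01-D21 (21 days) plus D22-D43 (22 days) gives 43, with no overlap and no gap. Pre-injection events on D22 go back to dose 1 through the visit field. Relative to dose 1 their onset day is 22 − 1 + 1 = 22, still inside the first dose's 21-day window.

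**Size.** The SAP gives no rate for same-day events. Assuming 1 to 3 affected participants among 515:
- 1/515 = 0.19%
- 3/515 = 0.58%

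This is the gain in the dose 1 row.

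**The case against.** The strongest defence is that the passages can be read together. Section 4.2.1.2 brings SAEs, AESIs and MAAEs under the last-vaccination rule, so that rule already decides same-day events. The words about including the day of dose 2 may be there only to give a home to events before the injection, which do belong to dose 1. This reading is plausible and may be what the sponsor intends. But none of the three subsections states it or refers to section 4.2.1.2.3, and the wording as it stands takes in the whole day.

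A reader might infer more than the text supports, on four counts:

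- **That dose 2 would look safer.** This does not follow. The 21-day definition in section 4.2.1.2.4 keeps the event in the dose 2 row. It would be lost there only if the day-1 convention were not applied to that row.
- **That an acute signal could disappear.** It would not. Immediate unsolicited systemic AEs within 30 minutes of each vaccination are a separate endpoint (section 3.4.3). The unsolicited AE tables assign the event to dose 2. Time of onset and relationship to vaccination are also reported for SAEs, AESIs and MAAEs.
- **That the booster's safety is judged against the dose 2 profile.** No section says so. The Comparator is the reference for the immunogenicity hypotheses; safety is described with percentages and confidence intervals.
- **That dose rows summing to more than the combined row are wrong in themselves.** For percentages of participants they are not, because one person can have separate events in both periods. The error is that a single event is counted twice.

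**Conclusion.** The point holds in a limited form. As written, the first period includes post-injection events on the day of dose 2, which the SAP's own rules assign to dose 2. Read literally, such an event is counted in both dose rows and the dose 1 row is inflated.

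The effect is confined to the by-dose split of rare events in descriptive tables for one group. The combined D01 to 21 days post dose 2 row and the entire-study row do not change. The booster arms receive one injection and are not affected. The primary safety endpoints for these event types are defined over the whole study, and no hypothesis test uses the split.

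The 0.19 to 0.58 percentage points rest on an assumed 1 to 3 affected participants and on the planned 515. With fewer participants enrolled, each event would weigh more. The one-day overlap itself rests only on the SAP's day count. The change is worth making before the tables are programmed because it removes a double count at no cost, not because any conclusion of the trial depends on it.

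**What to change.** In sections 4.2.1.2.6, 4.2.1.2.7 and 4.2.1.2.8, for the Comparator Group:

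1. End the first period at the dose 2 injection. Keep the existing fallback of 21 days after D01 for participants who do not receive dose 2.
2. Start the second period at the dose 2 injection, with that day as day 1, and state that it runs through onset day 22 as in section 4.2.1.2.4.
3. Assign events that start on the day of dose 2 by the 'Appeared after Visit' rule, with a cross-reference to section 4.2.1.2.3.

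Each event then falls in one dose period only, and the two periods together make up the combined one. If the sponsor always meant pre-injection events only, the same edit states that intent. The cost is a wording change in three subsections. The field is already used for the other AE tables, so no new data are needed.

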4.2.1.2.8 Adverse Events of Special Interest

An event will be considered as an AESI if “Yes” is checked for “Is the event an AESI?” in the CRF. AESIs will be analyzed throughout the study using the following periods:

For Supplemental Cohort 1 and Cohort 2 booster arms:

- From D01 to 21 days post dose 1
- During the 6 months follow up period
- During the entire study (ie, all AESIs occurred during the study)

For Supplemental Cohorts Comparator group:

- D01 to dose 2 (including the day of dose 2, use 21 days after D01 if dose 2 is not received)
- Within 21 days post dose 2

- From D01 to 21 days post dose 2
- During the 6 months follow up period
- During the entire study (ie, all AESIs occurred during the study)

Note: AESI that occurred before vaccination (negative time of onset) will not be included in analysis but will be listed separately.

Main analysis and complementary analysis will be applied for AESIs.

4.2.2 Other Safety Endpoints

For the safety endpoint related to SARS-CoV-2 infections (endpoints from [Section 4.2.2.1](#) to [Section 4.2.2.7](#)), main analysis will be applied including only those cases with start date before a participant received a non-study authorized/approved COVID-19 vaccine if applicable. Other cases with start date reported in participants after the receipt of an authorized/approved COVID-19 vaccine will be listed separately.

4.2.2.1 Laboratory-Confirmed SARS-CoV-2 infection

Laboratory-confirmed SARS-CoV-2 infection is defined as a positive result for SARS-CoV-2 by NAAT (done by the central laboratory [Section protocol section 8.3.3] or locally [Local Test for COVID-19 page in CRF]) on at least one respiratory sample collected throughout the study.

4.2.2.2 Serologically-Confirmed SARS-CoV-2 infection

Serologically-confirmed SARS-CoV-2 infection is defined as a positive result in a serum sample for antibodies specific to the Nucleocapsid of SARS-CoV-2 detected by electrochemiluminescence immunoassay (ECLIA) collected throughout the study.

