At the CLI01 visit, participants will be provided with a pulse oximeter and asked to record pulse oximetry readings twice a day from onset of illness until the results of the respiratory swab collected for NAAT testing at CLI01 are available. Continuation of pulse oximetry readings by the participant after availability of test results will be based on Investigator judgment.

‡ Follow-up telephone call approximately 30 days after onset of illness. If symptoms are ongoing 30 days after illness onset, a second telephone call 60 days after onset of illness will be scheduled.

Table 1.2: Planned sample sizes for Supplemental Cohorts 1 and 2

		Cohort 1	Cohort 2 Main Arms			Comparator *
		Booster	Booster	Booster	Booster	Primary Series
		CoV2 preS dTM-AS03 (D614)	CoV2 preS dTM-AS03 (B.1.351)	CoV2 preS dTM-AS03 (D614 + B.1.351)	CoV2 preS dTM-AS03 (D614)	CoV2 preS dTM-AS03 (D614)
Total Overall		565	970	865	345	515
SARS-CoV-2-naïve, Unvaccinated Adults (18-55 years)						515
Pfizer/BioNTech	Adults (18-55 years)	215	515	515	--	
	Older adults (≥ 56 years)	50	50	50	--	--
CoV preS dTM-AS03 (Original Phase II Cohort)	Adults (18-55 years)	--	30	--	270	--
	Older adults (≥ 56 years)	--	75	--	75	--
Moderna	Adults (18-55 years)	75	75	75	--	--
	Older adults (≥ 56 years)	25	25	25	--	--
Oxford University/ AstraZeneca	Adults (18-55 years)	75	75	75	--	--
	Older adults (≥ 56 years)	25	25	25	--	--
J&J/Janssen	Adults (18-55 years)	75	75	75	--	--
	Older adults (≥ 56 years)	25	25	25	--	--

Table 1.3: Planned sample sizes for Supplemental Cohort 2 Exploratory B.1.351 Arms

		CoV2 preS dTM-AS03 (B.1.351) Treatment Groups			
		2.5 µg with full-dose AS03	5 µg with half-dose AS03	5 µg with no adjuvant	2.5 µg with half-dose AS03
Total Overall		100	100	100	100
Age Groups	Adults (18-55 years)	75	75	75	75
	Older adults (≥ 56 years)	25	25	25	25

Supplemental Cohort 1 and Cohort 2 Booster Arms Only: all participants will receive a single booster dose (VAC) at D01. Blood samples will be collected from all participants prior to the booster injection, 14 days, 1 month, 3 months, 6 months, and 12 months after the injection.

Supplemental Cohorts Comparator Group: all participants will receive 2 vaccine injections given 3 weeks apart: the first injection will be at D01 (VAC1) and the second injection will be at D22 (VAC2). Blood samples will be collected from all participants prior to each injection, 14 days, 4 months, 6 months, 9 months, and 12 months after last injection.

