3.3 Populations for Analyses

The following subgroup definitions of SARS-CoV-2 Naïve and Non-Naïve at D01 timepoint are applied for all randomized participants in all Supplemental Cohorts:

Prior SARS-CoV-2 infection status	Description
SARS-CoV-2 Naïve at baseline (Naïve-D01)	
• Negative by the anti-S immunoassay (Roche Elecsys) on D01 serum sample 
AND
 
• Negative NAAT for SARS-CoV-2 on respiratory sample collected on D01
SARS-CoV-2 Non-Naïve at baseline (Non-Naïve-D01)	
• Positive by the anti-S immunoassay (Roche Elecsys) on D01 serum sample 
OR
 
• Positive NAAT for SARS-CoV-2 on respiratory sample collected on D01

The following subgroup definitions of SARS-CoV-2 Naïve and Non-Naïve at both D01 and D22 timepoints are applied for all randomized participants in Supplemental Cohorts comparator groups:

Prior SARS-CoV-2 infection status	Description
SARS-CoV-2 Naïve at second injection (Naïve-D01+D22)	
• Negative by the anti-S immunoassay (Roche Elecsys) on D01 serum sample 
AND
 
• Negative NAAT for SARS-CoV-2 on respiratory sample collected on D01 and D22
SARS-CoV-2 Non-Naïve at second injection (Non-Naïve-D01/D22)	
• Positive by the anti-S immunoassay (Roche Elecsys) on D01 serum sample 
OR
 
• Positive NAAT for SARS-CoV-2 on respiratory sample collected on D01 or D22

The following populations are defined for analysis:

Population	Description
Screened	All participants screened for potential study enrollment will be included regardless of being enrolled or not being enrolled. The screening includes the SARS-CoV-2 rapid serodiagnosis test results, demographic information (age, ethnic/racial population, high-risk medical conditions), inclusion/exclusion criteria and prior vaccination platform for booster vaccination groups. The participants reaching the enrollment cap identified in IRT will be excluded from the study enrollment and will have no participant ID assigned.
Randomized	All participants with a randomized group that have been allocated by IRT.

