3.4.5 Secondary Endpoints - Safety

The occurrences of laboratory-confirmed symptomatic COVID-19 and serologically-confirmed SARS-CoV-2 infection will be described by percentages of participants with infection during the analysis period with 95% CI by Clopper-Pearson methods.

Participants with active SARS-CoV-2 infection at baseline (as determined by positive NAAT at D01) will be listed separately, if applicable.

If the total number of observed COVID-19 clinical illness cases collected during the analysis period is less than 5 in all groups, no summary analysis will be performed, and a listing of observed cases will be provided.

For Supplemental Cohorts Comparator group, laboratory-confirmed symptomatic COVID-19 and serologically-confirmed SARS-CoV-2 infection that occurred after authorized/approved COVID-19 vaccine injection will be listed separately.

For Supplemental Cohort 1 and Cohort 2 booster arms, laboratory-confirmed symptomatic COVID-19 and serologically-confirmed SARS-CoV-2 infection that occurred after authorized/approved COVID-19 vaccine injection during the study period will be listed separately.

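### Serologically-confirmed infection is defined without a negative D01 anti-N result, so resolved infections that predate the study injection count as on-study cases

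*SAP*

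**What the plan says.** Section 4.2.2.2 gives the case definition: "Serologically-confirmed SARS-CoV-2 infection is defined as a positive result in a serum sample for antibodies specific to the Nucleocapsid of SARS-CoV-2". The sample may come from any point in the study. The section does not ask for a negative earlier sample and does not exclude the D01 draw. That draw exists for every boosted participant (Section 1, text after Table 1.3): "Blood samples will be collected from all participants prior to the booster injection".

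Section 3.4.5 reports serologically-confirmed infection together with laboratory-confirmed symptomatic COVID-19. These "will be described by percentages of participants with infection during the analysis period with 95% CI by Clopper-Pearson methods". Its only provision for baseline status is: "Participants with active SARS-CoV-2 infection at baseline (as determined by positive NAAT at D01) will be listed separately, if applicable".

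Section 4.2.2 keeps in the main analysis those cases that start before any non-study COVID-19 vaccine. It sets no lower limit at the study injection. Section 4.2.2.3 defines a start date for symptomatic illness, but no section defines one for a serological case. Section 4.2.2.4 defines SARS-CoV-2 infection as serologically or laboratory confirmed, so it inherits the same rule.

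Section 3.3 classifies prior infection status in all Supplemental Cohorts. One of the two routes to non-naïve is "Positive by the anti-S immunoassay (Roche Elecsys) on D01 serum sample"; the other is a positive D01 NAAT. Table 8.1 lists the anti-S assay and NAAT for this purpose. It lists no anti-N assay and no anti-N timepoints.

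**The concern.** A participant infected before enrolment and since recovered can be N-positive and NAAT-negative at D01. That person meets Section 4.2.2.2 on the D01 sample, or on a later one if N antibody persists, and is not removed by Section 3.4.5. The reported percentage then mixes prevalence at entry with incidence during follow-up, although it is labelled as infection in the analysis period. A reader would take it as the rate of infection after the study vaccine.

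The Section 3.3 classification cannot be used to separate the two in the booster arms. Those participants are already vaccinated, so a positive anti-S result is expected from priming and does not indicate infection. This is an inference from the population; the SAP does not discuss it.

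**Working it through.** The SAP states no figure that depends on this definition, so there is none to reproduce. The check has two parts.

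**1. Do the rules together exclude a resolved earlier infection?**

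| Rule | Section | Excludes a resolved infection? |
|---|---|---|
| N-positive serum sample at any time in the study | 4.2.2.2 | No; no negative baseline needed |
| Percentage over the analysis period | 3.4.5 | Intent only; no rule says when a serological infection began |
| D01 NAAT positives listed separately | 3.4.5 | No; covers active infection only |
| Start date before a non-study vaccine | 4.2.2 | No; upper limit only, and no start date is defined for a serological case |
| Naïve/non-naïve by anti-S and NAAT | 3.3 | No; not linked to this endpoint and uninformative after priming |

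None of them does. The start-date rule also cannot be applied to a serological case as written.

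**2. How large could the effect be?**

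Inputs: N = 565, the planned Cohort 1 booster total (Table 1.2). Let p be the share N-positive and NAAT-negative at D01, and q the on-study N-seroconversion rate among those N-negative at D01. Both are assumptions, since the SAP gives neither. All D01 N-positives are taken as counted, which follows if D01 serum is tested for anti-N.

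- Counted proportion as written: p + (1 − p)q
- New infections only: (1 − p)q
- Share of counted cases that predate the booster: p / [p + (1 − p)q]

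For p = q = 5%: 0.05 + 0.95 × 0.05 = 0.0975. This gives 565 × 0.0975 = 55 counted and 565 × 0.0475 = 27 new, so 0.05 / 0.0975 = 51% predate the booster.

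| p | q | Counted of 565 | New | Share predating |
|---|---|---|---|---|
| 2% | 20% | 122 | 111 | 9% |
| 2% | 5% | 39 | 28 | 29% |
| 5% | 5% | 55 | 27 | 51% |
| 10% | 5% | 82 | 25 | 69% |
| 20% | 10% | 158 | 45 | 71% |
| 30% | 2% | 177 | 8 | 96% |

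The first and last rows are the extremes over p = 2–30% and q = 2–20%.

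**Side question: the primary titers.** Suppose a share f of a booster arm was previously infected, with D15 titers a-fold and D01 titers b-fold those of the rest. The D15 GMT is multiplied by a^f and the post/pre GMTR by (a/b)^f. With f = 20% and a = 3 (assumed), 3^0.2 = 1.246, or 0.095 log10. With f = 10% and a = 2, 2^0.1 = 1.07. For scale, the non-inferiority margin is log10(1.5) = 0.176. The GMTR falls whenever b exceeds a, so the two co-primary endpoints can move in opposite directions.

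**The case against.** The strongest reply is that little depends on this endpoint. Table 2.1 does not list serologically-confirmed infection among the secondary safety endpoints. It is a descriptive percentage, enters no hypothesis test, and is described as covering the analysis period, which suggests that new infections were meant. All of that stands and limits the point's importance. It does not supply the missing derivation rule.

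Four stronger readings are tempting, and the document does not support them:

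- **Inflation differs by arm.** This is not shown. The Cohort 2 main arms are randomized within priming-vaccine and age strata, so baseline N-positivity should be balanced between randomized arms. Safety uses the SafAS for all groups without a naïve restriction. Section 5 says the baseline rapid test has low sensitivity for identifying naïve participants, so the comparator may also contain earlier infections.
- **Prior infection in the booster arms is never identified.** D01 NAAT identifies active infection. The protocol is not at hand and may address infection history, eligibility or D01 anti-N testing.
- **An unrestricted booster set against a naïve-only comparator in Table 3.2 is an error.** It is the stated design. The Table 2.1 objectives compare boosted vaccinees with a primary series in naïve individuals and do not call for infection-naïve boosters. Section 3.2.1 openly draws its booster assumptions from non-naïve data.
- **The primary conclusion is biased toward non-inferiority.** No prevalence or titer effect is given. The primary objective also needs a post/pre ratio above 2, which higher D01 titers would work against. Even the 0.095 log10 illustration is about 27% of the Cohort 1 distance from assumed truth (1.5) to margin (1/1.5), which is log10(2.25) = 0.352. It is 54% of the 0.176 distance for B.1.351 in Cohort 2, where the assumed ratio is 1.

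The anti-S label is uninformative in the booster arms, but no specified booster analysis uses it. Section 3.4.3 makes naïve status a subgroup only in the priming groups.

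**Conclusion.** The concern holds for the case definition. Followed literally, Sections 4.2.2.2, 3.4.5 and 4.2.2 count resolved pre-injection infections as on-study cases and carry them into the Section 4.2.2.4 composite. Symptomatic, hospitalized and severe COVID-19 rest on NAAT and are unaffected, as are the primary tests.

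The size depends wholly on baseline N-prevalence, which the SAP does not give. Over the assumed ranges, between 9% and 96% of counted cases would predate the booster, and about half at 5% and 5%. If D01 serum is not tested for anti-N, only those still N-positive at a later sample would be miscounted, so the figures would be lower.

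For the primary immunogenicity endpoints, prior infection in the booster arms is an unexamined influence of unknown size that could go either way. It is not a demonstrated bias.

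**What to change.** **Case definition (Sections 4.2.2.2 and 3.4.5).** Define a case as N-negative at D01 and N-positive at a later sample. Date it at the first positive sample, so that the Section 4.2.2 start-date rule can be applied. Use D01 N-negative participants as the denominator and list D01 N-positives separately. Carry the same rule into Section 4.2.2.4 and add the anti-N assay with its timepoints to Table 8.1.

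**Prior infection status (Section 3.3).** For previously vaccinated booster participants, define it by D01 anti-N or D01 NAAT.

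**Sensitivity analysis.** Where D01 anti-N results exist, add a supportive analysis of the primary GMT ratio and GMTR that excludes D01 N-positive booster participants. The main analysis stays as planned.

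**Cost.** If D01 anti-N results exist, this takes SAP wording and one supportive table. If not, D01 serum would have to be tested, and Table 8.1 does not settle which applies. The statistical price is a smaller denominator: of 565, it would be 565 × 0.95 = 537 at an assumed 5% baseline prevalence, or 565 × 0.80 = 452 at 20%, with correspondingly wider intervals.
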